## Study-Specific Adverse Event Capture and Data Safety and Monitoring Plan

Based on previous similar research with internet-based behavioral treatment conducted with survivors who have recovered from acute treatment effects and are living independently, this study is not expected to have Serious Adverse Events (SAE). We will contact and collect data from participants at baseline, 6-weeks, 3 months and 12 months. We plan ongoing recording of adverse events for each participant, each reviewed by the PI within 7 days. Any SAE will be immediately reported to the PI and the IRB according to requirements in the standard Fred Hutch DSMP. As Coordinating Center, Fred Hutch will complete the Fred Hutch/UW Cancer Consortium Expedited Reporting Form for all adverse events, including those associated with participants enrolled from the participating consortium centers. Ad hoc meetings will be called by the PI for any SAE, for two similar Adverse Events, or at any time by any other study staff or investigator for a data or participant safety concern. A physician member of the research project will provide the medical monitoring for all adverse events. Adverse events and SAE will be reviewed annually by the Fred Hutch standing Data Safety and Monitoring Board and Institutional Review Board in addition to the immediate reviews for SAE just described.

3 = Additional treatment is needed, treatment recommendations are defined and an Investigator is designated to facilitate finding treatment if the participant is willing.

4 = If participant or other person's safety is in question, the PI/Project Director will determine whether a treating physician needs to be contacted to maintain safety. If so, an Investigator will be designated to make that contact and to follow-up to determine the outcome.

A notation will be made as to whether the adverse event resulted in the patient terminating the study.

3. The PI or Project Director will complete an SAE form and fax it to the Fred Hutch DSMB and IRB within 48 hours of receipt of the form and within 7 days of when the event becomes known.
4. Within 7 days of any non-serious adverse event during the study, the Investigator or study personnel observing or first being told of the event will fill out this form and fax it to the Project Director.

5. At each weekly team meeting, a regular agenda item will be to review Adverse Events. Documentation of no events or the nature of events will be included in team meeting minutes. Adverse Event forms will be sent to all site PIs and their Study Coordinators for their use, although we do not expect AEs from contacting the survivors for participation. Adverse Event forms will be retained, tallied and reported annually to appropriate agencies by the Study Coordinator.
6. All Adverse Event Forms and SAE will be reviewed annually by the Fred Hutch standing DSMB. At this time, they will prepare an adverse events summary to send to all Investigators and in annual reports. To reduce the likelihood of a similar occurrence the PI will schedule further discussion between staff if an adverse event is related to the study and is grade 2 or higher. This plan, as well as a summary of adverse events and copies of the SAE forms completed since the last renewal, will be reported to the DSMB, IRO and NCI program officer annually. Forms will then be filed with the patient's confidential data, without identifiers.

## 11.0 DATA CONFIDENTIALITY

Only code numbers will be used on data. Only staff who have been trained in human subjects protection and have signed confidentiality statements will have access to study information. All hard copy data is stored in locked file cabinets in locked offices. All data will be locked and password or keycard protected at all times. All computerized data files will be password protected with passwords requiring regular updating. All clinical computing internet-related electronic data will be maintained on a secure web fileserver with backup and protection against unauthorized access, as with other computer databases. Access to the database and programs will be controlled through requirements for unique accounts and passwords. Passwords will have a limited expiration life and will need to be reset quarterly for continued use. The contents of the secure web server including program source code, web site information and data will be written to backup media daily. Additionally, the study will have a secure online site, using the Clinical Oncology Research Entrance (CORE), for file and data sharing with Clinical Data Systems and Clinical Research Data Systems and across transplant centers.

The Clinical Data Systems department will provide server security. All electronic data will be maintained on a secure internet fileserver with backup and protection against unauthorized access. Access to the database and programs will be controlled through requirements for unique accounts and passwords. The contents of the secure internet server including program source code, internet site information and data will be written to backup media daily. All hard copy data will be stored in locked file cabinets in locked offices, without personal identifiers.

## 12.0 STATISTICAL CONSIDERATIONS AND DATA MANAGEMENT

### Projected Target Accrual for Randomized Study ETHNIC AND GENDER DISTRIBUTION CHART

Table 2. Anticipated/Planned Enrollment for Entire Randomized Study* Number of Participants ( must provide exact numbers. i.e. no range )				Non- Randomized Participants*
Ethnic Categories	Sex/Gender			
	Females	Males	Total	Total
Hispanic or Latino	15	15	30	6
Not Hispanic or Latino	242	240	482	144
Ethnic Categories: Total of All Participants*	257	255	512	150
Racial Categories				
American Indian/Alaska Native	3	2	5	3

Asian	6	6	12	2
Native Hawaiian or Other Pacific Islander	2	2	4	0
Black or African American	16	10	26	11
White	230	235	465	134
Racial Categories: Total of All Participants *	257	255	512	150

## Design

**Enrollment.** We expect to approach 1358 potentially eligible survivors who are between 2-5 years after HCT. Of these, 100 will be run-in approaches with a projected 20 enrolled and randomized, but not included in analyses. We project enrolling an additional N=492 eligible for a two-arm randomization to reach the sample sizes needed for each of the two primary endpoints. An additional projected 100 are expected to register and consent for the study, but either not complete baseline assessment required for randomization or to not be eligible for randomization after baseline assessment because of treatment in the past two years or other exclusion criteria. They will be given access to the INSPIRE site as a courtesy. We expect another group of 50 participants will consent but will not be eligible for randomization due to incomplete baseline assessment.

**Randomization.** Those with one or more targeted complications will be randomized to one of 2 arms (Group 1). Those without targeted complications will be separately randomized to one of 2 arms (Group 0). We expect approximately 305 will be eligible for Group 1 randomization and inclusion in one or more of the analyses of the 2 primary outcomes. To have sufficient power for each of the two primary endpoints, we will need to enroll 197 participants for the elevated distress outcome and 239 for the cardiometabolic non-adherence. Participants who do not qualify for analysis of either primary endpoint (Group 0) will be important for inclusion in secondary analyses and will also be randomized to intervention vs. control arms. Based on our experience in the previous internet grant, we project a loss of about 28% in the course of the study implementation from consent to 12-month assessment, 8% from mortality or severe medical problems. With 305 participants randomized to Group 1 for the primary analyses, this provides sufficient power for aims 1, 2, 3 and secondary analyses.

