**Cancer-Related Emotional Distress and Depression.** Cancer-related distress is a significant problem for HCT and other with a negative impact on quality of life.[6, 18] Distress is far more prevalent than clinical depression, with prevalence estimated at 43% in long-term HCT survivors and moderate to severe depressive symptoms in 13-15%. [7, 19-21] Distress can be due to many factors such as uncertainty, cGVHD, managing the side effects of transplant, and financial stress.[22-24] Our preliminary research found that 41% of 2-5 year HCT survivor study participants had elevated distress on the Cancer and Treatment Distress (CTXD) measure.[25] In the cohort of 936 study participants, all but 1% of those with elevated depression scores also had elevated distress on the CTXD, suggesting that the CTXD captures a large proportion of depressive symptoms.[11] Therefore, we believe our focus on CTXD distress as the primary outcome will also address depression needs for nearly all survivors, although we will still measure depressive symptoms as a secondary endpoint. Risk factors for distress for allogeneic HCT include younger age, shorter time after HCT, and cGVHD. For autologous HCT, comorbidities are a risk factor for distress.[26, 27] Pre-HCT depression predicts later depression and other poorer outcomes[6, 27] as well as survival.[6, 28, 29] We have demonstrated that the INSPIRE online program for HCT survivors can improve distress (see 2.2 Preliminary Research). Others have demonstrated improved distress and post-traumatic stress in HCT survivors with telehealth cognitive behavioral treatment.[30]

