## Endpoints

The primary endpoints to be evaluated for the above hypotheses are CTXD (distress) and HCA-cardio. The primary and secondary endpoints for the study will be defined as binary outcomes. Participants will qualify for analysis of a particular endpoint if they meet eligibility at their baseline response for that endpoint (CTXD  $\geq 0.9$  or HCA-cardio  $<80\%$  [primary endpoints], or HCA-cancer  $<80\%$  [secondary endpoint], PHQ-8 score  $\geq 10$ ). Some participants will contribute to both primary endpoint analyses, and others to none or one. Similar conditional analyses will be carried out for the secondary endpoints. Stepped-care telehealth will be introduced based on PRO assessed at 6-weeks, then short term outcomes will be assessed after 3 months and delayed or sustained effects will be assessed at 1 year.

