### Power Calculations

As described in Table 3, we expect to enroll a total of 492 subjects in order to attain the 197 and 239 participants needed to meet eligibility criteria for Group 1 randomization and inclusion in the intervention vs. control arm analyses of the 2 primary outcomes: dichotomous CTXD and cardiac HCA outcomes, respectively (some will be eligible for more than one). Among these, we estimate that 71 and 86 per arm will be available for analyses after the 12-month evaluation, respectively. Assuming control arm rates of events similar to or higher than those observed in the preliminary data from the INSPIRE study, these numbers of participants will allow us to detect a minimum relative risk of success for the intervention arm vs. the control arm of 1.9 for the CTXD and for the HCA-cardio endpoints, with 80% power and two-sided  $\alpha=0.025$  for each comparison ( $\alpha=0.05/2 = 0.025$  to conserve overall  $\alpha=0.05$ ). For evaluation of the continuous versions of the outcomes, we will have at least 80% power to detect a minimum effect size of 0.52, and 0.47 for the CTXD and HCA-cardio outcomes, respectively ( $\alpha=0.025$  for each).

Table 3. Sample size calculations for Aim 1 primary outcomes, 80% power

### Analysis Plan for Hypothesis 1

The primary endpoints to be evaluated for hypothesis 1 are distress score (CTXD) and the proportion of HCA-cardio within the past 12 months as reported on the HCA and will be defined as binary outcomes.

Participants will meet the primary endpoint for lack of distress if they score <0.9 on the CTXD. They will

meet the HCA-cardio endpoint if their percent of recommended screenings obtained within the past 12 months is  $\geq 80\%$ . The number and pattern of missing variables will be summarized and assessed to understand potential biases. If attrition is greater than 10% before the 12-month follow-up, we plan to utilize multiple imputation of the primary outcome and to carry out sensitivity analyses of the impact of missing data on the comparisons between study arms.[173]

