For Hypothesis 1, the two primary endpoints, evaluated at the 12-month time point among the subjects identified at baseline as impaired for that particular endpoint criteria will each be compared between study arms as intent to treat analyses using standard logistic regression analyses, adjusted for cancer center and utilizing a two-sided  $\alpha=0.025$  level of significance to preserve type I error at 0.05 overall for the two primary endpoints. If other factors appear to be imbalanced between study arms, we will adjust analyses for those factors. Secondary analyses will evaluate depression alone, a PHQ-8 score  $\geq 10$  (essentially a subset of those with distress) and HCA-cancer in a similar manner as carried out for the primary endpoints. Continuous versions of the tests comprising the primary and secondary endpoints using linear regression models as well as adjusting or stratifying on engagement with the intervention (viewing at least 3 pages of the online program or completing telehealth calls) will also be carried out. Assumptions regarding normality of the outcomes will be assessed, although examination of outcomes in preliminary data suggests this is a reasonable assumption, with no significant skew in the distributions. If assumptions are not met, appropriate transformations will be implemented or alternative methods explored (e.g. non-parametric methods).

### Hypothesis 2

Characteristics of intervention arm participants at the 6-week interim assessment who require telehealth stepped care because they 1) do not meet criteria for adequate knowledge of subsequent malignancy and cardiometabolic risks, or 2) do not report improved distress, or 3) have not logged in to the online program will include those with higher depression or distress scores at baseline, more health care barriers at baseline, age 70+ years, male sex, people of color, lower income and education.

### Analysis Plan for Hypothesis 2

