Among subjects in Group 0 and Group 1 intervention arms, we will define the endpoint as a binary indicator of whether the individual required telehealth stepped care at the 6-week time point. We plan to use generalized linear models to evaluate associations between patient characteristic variables and likelihood of stepped care. Variables to be examined include age (<70 vs. 70+ years), sex, race/ethnicity (White non-Hispanic vs. Non-White or Hispanic), income ( $<\$40,000$  vs.  $\$40,000$  per year) and education (college graduate yes/no), PHQ8 depression  $>16$ , and Barriers to HCA  $> 0.45$ . The need for telehealth stepped care is not likely to be a rare event (rare being  $<10\%$ ) and thus odds ratios from a logistic regression model would not be good approximations of the relative risk (RR). Therefore, rather

	CTXD	HCA-Cardio	
Enroll/Consent/complete baseline	492	492	
T1: Eligible for specific endpoint	197	239	
3 mo. voluntary withdraw or mortality/illness (4%)	[8]	[10]	
3 mo. non-responders, able to respond at 12 mo. (15%)	[30 eligible for T4]	[36 eligible for T4]	
T3: 3 mo. completers (81%)	160	194	
T4: 12 mo. potential cohort	189	229	
12 mo. voluntary withdraw or mortality/illness (5% of T4)	[9]	[11]	
12 mo. non-responders (20% of T4)	[38]	[46]	
12 mo. completers (75% of T4, 72% of T1)	142	172	
	[71/arm]	[86/arm]	

than logistic regression we will likely use a log-link with Poisson error structure and robust sandwich variance estimates to directly estimate the more interpretable RR.[173] A multivariable model will be established using single-variable and step-up and step-down procedures with a liberal p-value for inclusion in the model ( $p<0.2$ ). Factors identified as significantly ( $p<0.05$ ) associated with the need for telehealth stepped care will be examined and based on the magnitude of the RR estimate and the prevalence of the particular patient characteristic, we will similarly examine indicators of response to the telehealth care based on continuous primary endpoints in that subgroup. This will establish a profile of types of survivors for whom modified approaches to care may be beneficial.

### Aim 3 and Plan for Aim 3

Determine resources that would be needed to sustain the intervention as a national HCT survivorship program if implemented through the CIBMTR/NMDP.

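### Section 12.2 asserts sufficient power beyond the two primary endpoints without a calculation, and the plan's own figures contradict it for depression

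*Combined protocol and SAP*

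**What the plan says.** The Randomization paragraph of Section 12.2 expects about 305 participants in Group 1 and concludes: "With 305 participants randomized to Group 1 for the primary analyses, this provides sufficient power for aims 1, 2, 3 and secondary analyses". It makes no exception and gives no effect size, event rate or alpha for anything beyond the primary endpoints.

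The power text in Section 12.7 and Table 3 deals with CTXD and HCA-cardio only: 71 and 86 completers per arm, 80% power at two-sided 0.025, detectable relative risk (RR) 1.9, detectable d 0.52 and 0.47.

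Depression is a planned comparison between arms: "Secondary analyses will evaluate depression alone", by the same methods as the primary endpoints. Section 12.4 restricts the analysis set: "Participants will qualify for analysis of a particular endpoint if they meet eligibility at their baseline response for that endpoint". For depression that means PHQ-8 of 10 or more. Section 2.1 gives "moderate to severe depressive symptoms in 13-15" per cent of long-term HCT survivors. Table 3 gives retention as "12 mo. completers (75% of T4, 72% of T1").

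Hypothesis 2 names people of color among the characteristics expected to predict a need for stepped care. Its analysis plan in Section 12.7 uses the intervention arms of both Group 0 and Group 1. Sections 7.6 (stepped care) and 8.1 (time points) confine stepped care and the 6-week assessment to Group 1 intervention participants.

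**The concern.** A group of 305 is not the denominator for every analysis that the sentence covers. Analyses conditional on baseline impairment, or on a minority characteristic within one arm, use a fraction of it. Depression is the smallest of the conditional endpoints, and nothing shows that its set is large enough.

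What is at stake is interpretation. Section 2.1 justifies distress as the primary outcome partly because it should also cover depression needs. With sufficient power on record, a non-significant PHQ-8 result could be taken as evidence of no benefit when the comparison had less than an even chance of detecting an effect of the size planned for distress. A non-significant race/ethnicity result in Aim 2 could be misread in the same way, and it feeds the profile of survivors who may need modified care.

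**Working it through.** **Reproducing the plan's figures**

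- Completers per arm: 197 × 0.72 / 2 = 70.9 and 239 × 0.72 / 2 = 86.0, matching 71 and 86.
- Continuous outcomes (noncentral t, non-centrality d√(n/2), 2n − 2 degrees of freedom, two-sided 0.025): n = 71 with d = 0.52 gives 79.6%; n = 86 with d = 0.47 gives 79.3%. Both agree with the stated 80%.
- Binary outcomes (pooled-variance test of two proportions): RR 1.9 gives 80% power if control success is about 28% (CTXD) or 25% (HCA-cardio). The documents do not state these rates.

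**Depression**

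- Eligible: 492 × 0.13 = 64.0 to 492 × 0.15 = 73.8.
- Completers per arm: 64.0 × 0.72 / 2 = 23.0 to 73.8 × 0.72 / 2 = 26.6.
- Detectable d at 80% power, two-sided 0.05: 0.84 to 0.78. The normal approximation 2.80 × √(2/n) gives 0.83 to 0.77.
- Power at d = 0.52: 41% to 46%.
- With no loss at all (32.0 to 36.9 per arm), 0.52 × √(n/2) − 1.96 = 0.12 to 0.27, so power would be about 55-61%. Attrition is not the main cause.

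For the binary endpoint, power = Φ[(|p1 − p2| − 1.96·SE0)/SE1], where SE0 is the pooled and SE1 the unpooled standard error. With control 0.30, intervention 0.57 and n = 23.0: (0.27 − 0.286)/0.141 = −0.12, so power is 45%. The control rate is an assumption, so a range is shown:

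| Assumed control success | Power for RR 1.9 at 23.0-26.6 per arm |
|---|---|
| 25% | 35-40% |
| 30% | 45-51% |
| 35% | 57-64% |
| 40% | 71-77% |

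**Aim 2, race/ethnicity**

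The 15% share is the recruitment minimum in Section 7.0. Table 2 is consistent with it: 47 non-White plus 30 Hispanic is at most 77 of 512, or 15%.

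- Group 1 intervention only: 305 / 2 = 152.5; × 0.15 = 22.9, against 129.6.
- Both groups' intervention arms: 492 / 2 = 246; × 0.15 = 36.9, against 209.1.

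Detectable RR for needing stepped care (80% power, two-sided 0.05), at assumed rates in the reference group:

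| Reference rate | 23 vs 130 | 37 vs 209 |
|---|---|---|
| 40% | 1.77 | 1.61 |
| 50% | 1.60 | 1.48 |
| 60% | 1.47 | 1.38 |

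**Other analyses under the same sentence**

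- HCA-cancer, 45% non-adherent (Section 8.2): 492 × 0.45 × 0.72 / 2 = 79.7 per arm; detectable d about 0.44.
- Continuous outcomes in all randomized: 492 × 0.72 / 2 = 177.1 per arm; detectable d about 0.30.
- Aim 2 by sex, assumed evenly split: about 76 vs 76 in Group 1, detectable RR 1.56, 1.44 and 1.34 at the same three rates.
- Aim 3 is described as descriptive, so power does not apply.

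**The case against.** Secondary endpoints with limited power are ordinary, no decision rule depends on this sentence, and the primary calculation reproduces. All of that stands, and it makes this a correction of wording and reporting, not of design.

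Four stronger readings are tempting and are not supported.

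- **That a stated power figure is wrong.** No figure is given for Aim 2 or any secondary endpoint. The fault is an assertion without a calculation.
- **That the secondary analyses as a class, or Aim 2 as a whole, are too small.** HCA-cancer lies between the two primary endpoints in size, the all-randomized analyses are larger than either, and Aim 2 examines several predictors in a model-building exercise with no single confirmatory race/ethnicity test.
- **That Aim 2 will have 23 people of color.** That count follows from Sections 7.6 and 8.1. The analysis plan in Section 12.7 implies about 37. The sections conflict, and 15% is a minimum.
- **That the prevalence applies to the 305, giving 14-16 per arm.** Section 2.1 says that nearly everyone with elevated depression also had elevated distress, so they fall within Group 1. The base is 492.

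It is also fair to say that 13-15% is a background prevalence and not a projection of baseline PHQ-8 here, and that the binary result depends on an unknown control rate. The first is the only figure that the plan offers. At 20% prevalence (about 35 per arm) the detectable d would still be about 0.68. On the second, power for RR 1.9 comes close to 80% only when control success is about 40%.

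**Conclusion.** The assertion is unsupported beyond the two primary endpoints, and for depression the plan's own inputs contradict it: about 23-27 completers per arm, detectable d about 0.78-0.84, and 41-46% power at d = 0.52. Power for RR 1.9 is 35-51% at 25-30% control success and 71-77% at 40%.

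The race/ethnicity predictor is thin on either reading of the Aim 2 population, with detectable RR 1.77-1.47 or 1.61-1.38 at reference rates of 40-60%. The conclusion does not extend to the other analyses sized above.

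It rests on 13-15% as a proxy for baseline PHQ-8 of 10 or more, 72% completion, 1:1 allocation, and two-sided 0.05, since the plan gives no alpha for secondary endpoints. At 0.025, power at d = 0.52 falls to about 30-35%. Control success and stepped-care rates are assumed ranges.

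**What to change.** 1. Limit the sentence in Section 12.2 to the two primary endpoints.
2. State for PHQ-8 the expected 23-27 per arm and the detectable effect, with the assumed range of control rates. Give the expected count and detectable RR for the Aim 2 race/ethnicity predictor.
3. Report depression as an estimate with a 95% confidence interval, not as a powered test.
4. Reconcile the Aim 2 population in Section 12.7 with Sections 7.6 and 8.1.

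The main depression comparison should stay as planned. A continuous PHQ-8 analysis in the CTXD-elevated set (71 per arm, detectable d about 0.47 at two-sided 0.05) could at most be supplementary. Only 64-74 of those 197, or 32-38%, would have PHQ-8 of 10 or more, so it asks a different question. If benefit were confined to them, an average d of 0.47 would need about 1.25-1.45 in that subgroup (0.47/0.375 to 0.47/0.325, same SD).

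The cost is a few sentences and a less favourable statement of power. No new data or extra participants are needed.
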